2.2 TRIAL OBJECTIVES

The primary objective is to assess long term safety of treatment with oral nintedanib in patients with Idiopathic Pulmonary Fibrosis (IPF).

Please refer to [Section 5](#) for a detailed description of the trial endpoints.

2.3 BENEFIT - RISK ASSESSMENT

Nintedanib has shown robust, reproducible, statistically significant, and clinically meaningful effects on the decline in lung function as measured by FVC. In two large, international, placebo-controlled phase III trials of identical design, nintedanib 150 mg bid statistically and clinically significantly reduced the annual rate of decline in FVC over 52 weeks compared with placebo indicating a relative difference of approximately 50% between nintedanib and placebo. This effect of nintedanib is considered consistent with slowing disease progression as measured by FVC.

The risks of treatment with nintedanib are primarily related to the gastrointestinal tract (nausea, vomiting, diarrhoea, abdominal pain) and to increases in liver enzymes (AST, ALT, ALKP, gamma-GT) and bilirubin. Also weight decrease and decreased appetite have frequently been reported in studies with nintedanib. Moreover, based on experience with other tyrosine kinase inhibitors, impairment of immune and of kidney function, intestinal perforations, increases in blood pressure as well as potential bleeding and thrombotic events should be carefully monitored and evaluated in clinical trials. In patients who develop severe symptoms of gastrointestinal toxicity not amenable to symptomatic treatment with standard measures, severe liver enzyme elevations, severe drug-related infections, or uncontrolled hypertension, treatment with nintedanib must be discontinued and appropriate therapeutic measures taken (refer to [Section 4.2.1.1](#)). Liver enzymes must be followed closely during treatment with nintedanib.

Proprietary confidential information.

© 2017 Boehringer Ingelheim International GmbH or one or more of its affiliated companies. All rights reserved.

This document may not - in full or in part - be passed on, reproduced, published or otherwise used without prior written permission.

The dose of nintedanib must be reduced to 100mg bid, or nintedanib must be discontinued in the event of hepatic toxicity and further treatment withheld until recovery of the abnormal laboratory parameters (refer to [Section 4.2.1.2](#)).

Patients with IPF may benefit from lesser decline in lung function and hence slower disease progression as a result of treatment with nintedanib. In addition, nintedanib may reduce the risk of acute IPF exacerbations and worsening of patient's quality of life. Finally, nintedanib may ultimately be found to reduce mortality. Overall, the benefit/risk profile of nintedanib, as established during the phase II and III trials is interpreted as favourable for the treatment of IPF.

Although rare, a potential for drug-induced liver injury is under constant surveillance by sponsors and regulators. Therefore, this study requires timely detection, evaluation, and follow-up of laboratory alterations of selected liver laboratory parameters to ensure patients' safety.

Patients who are offered to enter this open label extension trial must have participated in a phase III parent trial (1199.32 or 1199.34) for one year. All patients will be treated with active drug. Patients who have not tolerated the blinded study drug or discontinued for any reason are not eligible for the extension trial. Patients who were randomized to placebo in the parent trial will be receiving the active drug for the first time. Similar safety monitoring procedures as in the phase III trials will be applied.

The routine safety monitoring established in the parent study is considered appropriate for the long term follow-up of the patients. It consists of regular visits to the investigational site, blood analyses and specific monitoring procedures to follow-up potential hepatic enzyme elevation. In case it is considered adequate by the investigator, the dose of nintedanib may be reduced to 100 mg bid or dosing may be interrupted.

Proprietary confidential information.

© 2017 **Boehringer Ingelheim International GmbH** or one or more of its affiliated companies. All rights reserved.

This document may not - in full or in part - be passed on, reproduced, published or otherwise used without prior written permission.

3. DESCRIPTION OF DESIGN AND TRIAL POPULATION

3.1 OVERALL TRIAL DESIGN AND PLAN

This is a multi-centre, multi-national, prospective, open label extension clinical trial. It is planned to include approximately 750 patients with IPF who have completed 52 weeks of treatment and the follow up period of the phase III parent trials. Only patients enrolled in the parent trials (1199.32 and 1199.34) will be eligible.

After signing Informed Consent and if all eligibility criteria are met, patients will initiate treatment with nintedanib (Visit 2). Please refer to [Section 4.1.2](#) for the method of assigning patients to treatment groups.

Overall, the trial is estimated to last a total of approximately 6 ½ years. Treatment will be stopped if a reason for withdrawal is met (refer to [Section 3.3.4](#)).

Patients' participation starts once they have signed the Informed Consent form and it is concluded when they have undergone the Follow-up Visit (unless the patient is lost to follow up or informed consent is withdrawn). Adverse events are collected during all the trial period and are considered under treatment until 28 days after drug discontinuation.

3.1.1 Administrative structure of the trial

The trial is sponsored by Boehringer Ingelheim (BI).

BI has appointed a Trial Clinical Monitor (TCM), responsible for coordinating the activities required in order to manage the trial in accordance with applicable regulations and internal standard operating procedures (SOPs), directing the clinical trial team in the preparation, conduct, and reporting of the trial, ordering the materials as needed for the trial, ensuring appropriate training and information of Clinical Monitors Local (CML), Clinical Research Associates (CRAs), and investigators of participating countries.

Data Management and Statistical evaluation will be performed by BI according to BI SOPs. For these activities, a Trial Data Manager and a Trial Statistician have been appointed.

Tasks and functions assigned in order to organise, manage, and evaluate the trial will be defined according to BI SOPs. A list of responsible persons will be given in the Clinical Trial Master File (CTMF) document.

The organisation of the trial in the participating countries will be done by the respective local BI organisation (Operating Unit (OPU)) or by a Contract Research Organisation (CRO) with which the responsibilities and tasks will have been agreed and a written contract filed before initiation of the clinical trial. In each OPU participating in this study, a CML was appointed responsible for coordinating the activities required in order to manage the trial in accordance with applicable regulations and internal SOPs in the countries covered by the respective BI OPU.

Proprietary confidential information.

© 2017 Boehringer Ingelheim International GmbH or one or more of its affiliated companies. All rights reserved.

This document may not - in full or in part - be passed on, reproduced, published or otherwise used without prior written permission.

A Co-ordinating Investigator was nominated to coordinate investigators at different sites participating in this multicentre trial. [REDACTED] will review the trial protocol, any subsequent amendments to the protocol and the (draft) Clinical Trial Report (CTR). [REDACTED] will provide [REDACTED] signature on the final protocol signature page and amendments and will provide [REDACTED] signature on the (draft) Clinical Trial Report (CTR) indicating that, to the best of Co-ordinator's knowledge, the final CTR accurately describes the conduct and results of the Trial.

Trial sites consist of specialised referral centres experienced in the management of IPF. Documents on participating (Principal) investigators and other important participants, especially their curricula vitae, will be filed in the CTMF.

Details of the trial supplies including responsible institutions are given in [Section 4](#) of this protocol.

Central laboratory facilities will handle all laboratory analyses of the trial. In addition liver enzymes intermediate measurements may be performed in a local laboratory or at a local doctor's office using specific laboratory kits supplied for the study that will be analysed centrally.

To assure the standardisation of PFTs, the lung function equipment for spirometry will be provided by the sponsor (refer to [Section 5.2](#)).

The ISF will be maintained at the sites as required by local regulation and BI SOP. A copy of the ISF documents will be kept as an electronic CTMF document according to BI SOPs.

3.2 DISCUSSION OF TRIAL DESIGN, INCLUDING THE CHOICE OF CONTROL GROUP

The trial will be conducted as a prospective, open-label design with the objective to collect long term safety data on nintedanib in patients with IPF. The observation period will extend until either every patient is discontinued or a reason for stopping the trial is met (refer to [Section 3.3.4](#)). Patients who have completed one year treatment plus follow-up period in a parent trial are eligible for participation.

The purpose of this trial is to offer the option to all patients who completed the randomized phase III trial 1199.32 or 1199.34 to receive nintedanib treatment if they perceive an individual benefit. The decision to continue treatment will be made by the patient following a discussion with the investigator. The aim of the study is to allow treatment continuation to individual patients; therefore, randomization, blinding and use of placebo would not be appropriate.

To obtain information on the long term safety and tolerability of nintedanib, adverse events and acute IPF exacerbations will be reported, and clinical laboratory tests, electrocardiograms and lung function tests will be performed. FVC derived endpoints will be assessed and data on discontinuations and death will be recorded.

Proprietary confidential information.

© 2017 Boehringer Ingelheim International GmbH or one or more of its affiliated companies. All rights reserved.

This document may not - in full or in part - be passed on, reproduced, published or otherwise used without prior written permission.

The chosen endpoints are a subset of the endpoints used in the parent trial; no new endpoint is introduced in this trial.

3.3 SELECTION OF TRIAL POPULATION

It is anticipated that approximately 750 patients will complete 52 weeks of treatment with nintedanib or placebo and the follow up period in the phase III trials 1199.32 and 1199.34 (assuming a similar drop-out rate as in the phase II). These patients will be allowed to participate in this extension trial. Patients previously on active treatment will continue; patients who received placebo in the parent trial will initiate treatment with nintedanib for the first time at Visit 2.

A log of all patients included in the study (i.e. having given informed consent) will be maintained in the ISF at the investigational site irrespective of whether they have been treated with investigational drug (i.e. open label nintedanib) or not.

3.3.1 Main diagnosis for study entry

Patients with IPF are eligible for inclusion if they fulfil all the inclusion criteria ([Section 3.3.2](#)) and do not present any of the exclusion criteria ([Section 3.3.3](#)).

In general patients who have completed the parent trial are eligible. However treatment interruption between the parent trial and the extension open label study should not be > 12 weeks. Patients who had experienced adverse events in the parent trial but were allowed to continue receiving blinded study medication either at 150 mg bid dose or at the reduced dose level 100 mg bid, will be offered participation in the extension trial.

3.3.2 Inclusion criteria

1. Signed Informed Consent consistent with ICH-GCP and local laws prior to trial participation.
2. Patients from trials 1199.32 or 1199.34 who completed the 52 weeks treatment period and performed the follow-up visit.

3.3.3 Exclusion criteria

1. AST, ALT > 1.5 fold ULN

Patients who completed the parent trial with transaminase values > 1.5 fold ULN but < 3 fold ULN are considered eligible.

2. Bilirubin > 1.5 fold ULN
3. Bleeding risk:

Proprietary confidential information.

© 2017 Boehringer Ingelheim International GmbH or one or more of its affiliated companies. All rights reserved.

This document may not - in full or in part - be passed on, reproduced, published or otherwise used without prior written permission.

- a. Patients who require fibrinolysis, full-dose therapeutic anticoagulation (e.g. vitamin K antagonists, dabigatran, heparin, hirudin), or high dose antiplatelet therapy. Exceptions: prophylactic low dose heparin or heparin flush as needed for maintenance of an indwelling intravenous device (e.g. enoxaparin 4000 IU s.c. per day) and prophylactic use of antiplatelet therapy (e.g. acetyl salicylic acid up to 325 mg/d, or clopidogrel at 75 mg/d, or equivalent doses of other antiplatelet therapy);
 - b. Hemorrhagic CNS event, gross / frank haemoptysis or haematuria, active gastro-intestinal bleeding or ulcers after completion of the parent trial;
 - c. Coagulation parameters: International normalised ratio (INR) > 2, prothrombin time (PT) and partial thromboplastin time (PTT) > 150% of institutional ULN.
4. Planned major surgery within the next 3 months, including lung transplantation, major abdominal or major intestinal surgery.
 5. New major thrombo-embolic events developed after completion of the parent trial:
 - a. Stroke;
 - b. Deep vein thrombosis;
 - c. Pulmonary embolism;
 - d. Myocardial infarction.
 6. Time period > 12 weeks between Visit 9 of the parent trial and Visit 2 of this study.
 7. Usage of any investigational drug after completion of the parent trial or planned usage of a specific investigational drug during the course of this trial.
 8. A disease or condition which in the opinion of investigator may put the patient at risk because of participation in this trial or limit the patient's ability to participate in this trial.
 9. Alcohol or drug abuse which in the opinion of the investigator would interfere with trial participation.
 10. Pregnant women or women who are breast feeding or of child bearing potential not using two effective methods of birth control (one barrier and one highly effective non-barrier) for at least 1 month prior to Visit 2 and/or not committing to using it until 3 months after end of treatment.

Women will be considered to be of childbearing potential unless surgically sterilised by hysterectomy or bilateral tubal ligation, or postmenopausal for at least two years. Highly effective methods of birth control include established use of oral, injected or implanted hormonal methods of contraception, placement of an intrauterine device

Proprietary confidential information.

© 2017 Boehringer Ingelheim International GmbH or one or more of its affiliated companies. All rights reserved.

This document may not - in full or in part - be passed on, reproduced, published or otherwise used without prior written permission.

(IUD) or intrauterine system (IUS). A barrier method of contraception includes condom or occlusive cap with spermicidal (foam, gel, film, cream, suppository) or male sterilization (with appropriate postvasectomy documentation of the absence of sperm in the ejaculate).

3.3.4 Removal of patients from therapy or assessments

3.3.4.1 Removal of individual patients

The treatment with nintedanib has to be permanently discontinued in the following circumstances:

- Liver function impairment (refer to [Section 10.1](#)):
 - ALT or AST \geq 8 fold ULN.
 - ALT or AST \geq 3 fold ULN for more than 2 weeks despite dose reduction.
 - ALT or AST \geq 3 fold ULN and total bilirubin $>$ 1.5 fold ULN.
 - ALT or AST \geq 3 fold ULN and INR $>$ 1.5.
 - ALT or AST \geq 3 fold ULN with the appearance of fatigue, nausea, vomiting, right upper abdominal quadrant pain or tenderness, fever, rash, and/or eosinophilia ($>$ 5%).
- Diarrhoea: reoccurrence of diarrhoea ($>$ 4 stools/day) for 8 or more consecutive days despite dose reduction and supportive care as described in [Section 4.2.1.1](#).
- Pregnancy (refer to [Section 5.3.7](#)).
- Planned usage of a specific investigational drug (refer to [Section 4.2.2.1](#)).
- Treatment interruption. Treatment interruption is acceptable in certain cases and for a defined period which are described in [Section 4.2.1](#).

Similar to the parent study, in the following cases withdrawal of study drug is highly recommended. Only in special circumstances, the investigator, upon thorough assessment of all available clinical data, and taking into consideration the potential risks associated with administration of nintedanib, may decide not to withdraw the patient, even though one or more of the below mentioned criteria are fulfilled. However, in such a case, continuation of study treatment should be discussed with the patient, and the decision documented in the source data.

Proprietary confidential information.

© 2017 Boehringer Ingelheim International GmbH or one or more of its affiliated companies. All rights reserved.

This document may not - in full or in part - be passed on, reproduced, published or otherwise used without prior written permission.

- Planned major surgery, including any major abdominal or intestinal surgery.
- Patients who require full-dose therapeutic anticoagulation (e.g. vitamin K antagonists, dabigatran, heparin, hirudin), or high-dose antiplatelet therapy.
- Major thrombo-embolic events e.g. stroke, deep vein thrombosis, pulmonary embolism, myocardial infarction.
- Increased risk of bleeding e.g. haemorrhagic CNS event, gross / frank haemoptysis or haematuria, active gastro-intestinal bleeding or ulcers.
- Deterioration of the disease. A ≥ 10 % decrease in the absolute value of FVC% predicted within 12 months is considered deterioration (progression of disease).

Patients have the right to withdraw from the study at any time without the need to justify the decision. The investigator has the right to remove patients from the study for non-compliance, administrative or other reasons.

Data of patients who discontinue or withdraw prior to medication assignment will be recorded in the eCRF. Data of patients who discontinue or withdraw after medication assignment must be documented and the reason for withdrawal must be recorded in the eCRF. The data must be included in the trial database and must be reported.

Refer to [Section 6.2.2](#) and [Section 6.2.3](#) for procedures to be followed for patients terminating the trial.

Patients who are discontinued from this trial are not allowed to be re-enrolled.

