4.2.1.1 Management of diarrhoea

The guidelines for managing diarrhoea are the same as in the parent protocols.

4-6 extra stools or i.v. fluid intake < 24 hours with no effect on daily living activities

Patients should be treated according to local standard (e.g. loperamide or equivalent).

If the severity of diarrhoea persists for 8 or more consecutive days despite optimal care, nintedanib treatment should be discontinued or reduced until return to less than 4 extra stools per day. Drug interruption is limited however to a maximum of 4 weeks and patients may restart treatment with nintedanib at a reduced dose (during a dose modification visit, refer to [Section 6.2.4](#)).

Dose re-escalation is allowed at any time after the beginning of the reduced dose if medically justified.

In case of re-occurrence of diarrhoea for 8 or more consecutive days despite dose reduction and after optimal or prophylactic therapy, patients have to permanently stop nintedanib and perform an End of Treatment Visit as soon as possible and a Follow-up Visit 28 days after last drug intake (refer to the [Flow Chart](#) for visit procedures).

> 6 extra stools or incontinence or i.v. fluid intake ≥ 24 hours or hospitalisation or decrease in daily living activities

Nintedanib has to be interrupted until return to less than 4 extra stools per day and patients should be treated with optimal supportive care (e.g. loperamide or equivalent). Thereafter, patients may restart treatment with nintedanib at a reduced dose.

In case of re-occurrence of diarrhoea for 8 or more consecutive days despite dose reduction and after optimal or prophylactic therapy, patients have to permanently stop nintedanib and perform an End of Treatment Visit as soon as possible and a Follow-up Visit 28 days after last drug intake (refer to the Flow Chart for visit procedures).

Proprietary confidential information.

© 2017 Boehringer Ingelheim International GmbH or one or more of its affiliated companies. All rights reserved.

This document may not - in full or in part - be passed on, reproduced, published or otherwise used without prior written permission.

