	C1	Incorrect trial medication taken	Medication kit assigned at visit 2 not matching treatment dose actually received by patient  or  Medication kit received at visit 2 does not correspond to the dose to be received according to CTP (150mg bid for patients on 150 bid in parent trial)  Automatic IPV	E
	C3	Overall Compliance not between 80% and 120% inclusive	Compliance <80% or >120%  Automatic IPV	E
	C4	Drug interruption longer than 46 days ; or 93 days in the case of acute exacerbations or unrelated AEs	Automatic IPV (reviewed in MQRM listings)	E
	C6	Dose Change not in agreement with the protocol procedures (see Section 4.2.1 of CTP)	Manual review of MQRMs listings	S
	C7	Drug not permanently discontinued despite criteria of Section 3.3.4.1 of CTP met	Manual review of MQRMs listings	S
D		Concomitant medication		
	D1	Prohibited medication use during the treatment period	
 
• Investigational therapy
 
• Full dose concomitant anticoagulation
 
• Fibrinolysis
 
• Antiplatelet therapy
 
 Manual review of MQRMs listings	S

Table 6.2: 1 Important protocol violations (cont'd)

E		Missing data		
	E4	Flow chart not observed for the planning of visit 1 and 2	Visit 1 and Visit 2 occurred on the same date whereas the period between Visit 9 of the parent trial and visit 1 is > 6 weeks.  Automatic IPV	S
F		Incorrect timing		
	F1	No adequate follow-up after liver enzyme elevation (see Table 10.1.1 of CTP)	Manual review of MQRMs listings	S

Automatic PVs are those detected via an automated programming process using SAS. Manual PVs are those identified during the MQRM meeting through patient listings and/or Manuel PV log.

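### The mandatory stop for recurrent diarrhoea does not say whether it counts total or extra stools, and it does not match the extra-stool scale of the management section under either reading

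*Protocol*

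**What the plan says.** Protocol 3.3.4.1 lists the circumstances in which nintedanib must be stopped for good. The diarrhoea item is "reoccurrence of diarrhoea ($>$ 4 stools/day) for 8 or more consecutive days despite dose reduction and supportive care", and it refers to section 4.2.1.1 for the dose reduction and supportive care. It contains neither the word total nor the word extra, and it mentions no usual habit.

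Protocol 4.2.1.1 expresses every stool count as extra stools:
- Lower band: "4-6 extra stools or i.v. fluid intake < 24 hours with no effect on daily living activities".
- Upper band: "> 6 extra stools or incontinence or i.v. fluid intake ≥ 24 hours or hospitalisation or decrease in daily living activities".
- Recovery level, stated in the lower band and used again in the upper: "nintedanib treatment should be discontinued or reduced until return to less than 4 extra stools per day".

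Both bands end with a permanent-stop clause that begins "In case of re-occurrence of diarrhoea for 8 or more consecutive days despite dose reduction and after optimal or prophylactic therapy". Neither clause gives a stool count.

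SAP 6.2, Table 6.2: 1, defines important protocol violation C7 as "Drug not permanently discontinued despite criteria of Section 3.3.4.1 of CTP met". It is classed as a safety violation and found by manual review of listings.

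**The concern.** The only number attached to the permanent stop stands in 3.3.4.1. Its unit is unstated, and the section it refers to counts on a different expressed scale. Nothing elsewhere in the protocol or SAP links the two. Two sites that see the same recurrence can therefore reach different decisions, each with support in the text.

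The decision has consequences for the patient and for the data:
- The stop is permanent, and a discontinued patient may not re-enrol (Protocol 3.3.4.1).
- Adverse events leading to discontinuation are a named component of the primary endpoint (Protocol 5.1.1).
- The SAP plans a diarrhoea table that includes drug discontinuation (7.8.1) and Kaplan-Meier plots of time to permanent discontinuation (7.7).
- C7 is judged against 3.3.4.1, so the reviewer of the listings meets the same ambiguity as the site.
- Section 3.3.4 still governs patients who continue after the lock for the final analysis (Protocol 6.2.5).

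**Working it through.** The plan states no figure of its own to reproduce. The check compares thresholds over whole-number daily stool counts.

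**Inputs**
- Stop count: more than 4 per day (Protocol 3.3.4.1).
- Lowest stool-count band: 4 or more extra; recovery: fewer than 4 extra (Protocol 4.2.1.1).
- Usual habit *h*: not given in the documents. Assumed range 0 to 4 stools per day.

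**Reading A: the stop counts total stools (the literal reading).** The stop begins at 5 per day whatever the habit. The lowest band begins at *h* + 4.

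| Usual habit *h* | Lowest band starts at | Stop starts at | Counts where the two differ |
|---|---|---|---|
| 0 | 0 + 4 = 4 | 5 | 4 (in the band, stop not met) |
| 1 | 1 + 4 = 5 | 5 | none |
| 2 | 2 + 4 = 6 | 5 | 5 (3 extra) |
| 3 | 3 + 4 = 7 | 5 | 5 and 6 (2 and 3 extra) |
| 4 | 4 + 4 = 8 | 5 | 5, 6 and 7 (1, 2 and 3 extra) |

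For habits of 2 to 4, each count in the last column meets the mandatory stop, is below the lowest stool-count band, and is under 4 extra, so it lies within the recovery level. At a habit of 0 the mismatch runs the other way.

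**Reading B: the stop counts extra stools.** The stop then begins at 5 extra, while the lowest band begins at 4 extra. A patient at exactly 4 extra is in the 4-6 band and has not recovered, but does not meet the stop. In total counts this is *h* + 4 for every habit: 6 per day at *h* = 2, 7 at *h* = 3.

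**Comparison.** Reading A gives a gap that depends on habit and vanishes only at 1 per day. Reading B gives a gap of one count at every habit. Neither makes the two sections agree throughout.

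**The case against.** The strongest reply is that 3.3.4.1 refers to 4.2.1.1, where every count is of extra stools, so its number is shorthand for extra stools. That reading is plausible, and it removes the habit-dependent conflict. It leaves the mismatch at exactly 4 extra, and it asks a site to supply a missing word in a mandatory rule.

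A second reply is that the recurrence clauses of 4.2.1.1 have no count, so 3.3.4.1 may simply fill the gap. The recovery level also governs return after an interruption or reduction, not recurrence on the reduced dose. This stands to the following extent. A reader might infer that one section orders a stop while the other tells the site to continue. The documents do not say that: 4.2.1.1 never instructs a site to continue such a patient. The defect is an undefined unit and threshold.

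Three other inferences go too far:
- That a patient in the gap is outside every management band. This holds on stool count alone, because the bands also admit patients on i.v. fluids, incontinence, hospitalisation or reduced daily activities.
- That a site following 4.2.1.1 will be recorded as a violator. C7 is a manual judgement, and SAP 6.2 says violations are only described and exclude nobody.
- That the problem is as large as the parent-trial diarrhoea rates of 61.5% and 63.2% (Protocol 1.2). Those count any diarrhoea. The affected group needs a recurrence on a reduced dose lasting at least eight days, at a count in a narrow gap. The phase II figure of 11.8% discontinuing for diarrhoea at 150 mg bid is closer in kind but still broader than this group.

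Investigators may also remove patients, and patients may withdraw, whatever the count.

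**Conclusion.** The point holds as an internal inconsistency in the wording of a mandatory stop. Under the literal reading, and assuming a habit of 2 or 3 stools per day, the sections diverge at 5, or at 5 and 6, stools per day; at a habit of 1 they agree. Under the extra-stool reading they diverge at exactly 4 extra. The assumed habits are mine, and literal does not mean proven: the text supports either reading.

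Sites can apply the permanent stop differently, and this can carry into discontinuations for adverse events and into the C7 review. An effect on the primary endpoint is possible but not shown. The number of patients cannot be estimated from the documents and is likely a small part of those with diarrhoea. All analyses are descriptive (Protocol 7.2), so no test or sample size is at risk. The matter should be corrected because the rule is mandatory and irreversible for the patient and the correction is simple. It does not threaten the trial's conclusions.

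**What to change.** Reconcile Protocol 3.3.4.1 and 4.2.1.1. The stop criterion and both recurrence clauses should state the same counting unit and the same recurrence threshold, in the unit used for the bands and the recovery level. The recurrence threshold and the recovery level need not be the same number. The unit and values are for the sponsor's clinical team, and this review takes no view on them. C7 in SAP Table 6.2: 1 should then be judged against the reconciled text.

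The change is one bullet and two clauses, plus a clarification to sites. Under Protocol 8.1 an amendment needs ethics committee and competent authority approval, so it is not free. If the unit chosen is extra stools, judging C7 also needs each patient's usual habit. The SAP mentions a diarrhoea page in the case report form but does not give its fields, so the sponsor should check whether habit is recorded.
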